## **6.10 Description of Activities Performed by Sponsor Representatives**

The Sponsor is responsible for selecting qualified investigators, obtaining a signed investigators’ agreement, and providing them with the information needed to conduct the investigation properly, ensuring the protection of human patients enrolled in the study, and identifying and distributing significant new information relevant to the investigation to the investigators. The Sponsor will evaluate circumstances where an investigator deviates from the CIP, and will retain the right to remove either the investigator or the investigational site from the study.

Trained Sponsor personnel will provide technical expertise and technical guidance on the use of the OPTIS system and Dragonfly Catheter, including training and proctored case coverage, as appropriate.

While Sponsor representatives may perform these activities, the Principal Investigator remains responsible for ensuring all clinical investigation data is collected as required per CIP.

## **6.11 Subject Study Completion**

Subject participation in the clinical investigation will conclude upon completion of the 24-month visit. Upon completion of subject participation in the clinical investigation, the subject will return to standard of care.

## **6.12 Subject Withdrawal**

Subjects must be informed about their right to withdraw from the clinical investigation at any time and for any reason without sanction, penalty or loss of benefits to which the subject is otherwise entitled. Withdrawal from the clinical investigation will not jeopardize their future medical care or relationship with the investigator. Subjects will be requested to specify the reason for the request to withdraw. The investigator must make all reasonable efforts to retain the subject in the clinical investigation until completion of the clinical investigation.

In case of subject withdrawal, the site should make attempts to schedule the subject for a final study visit. At this final study visit, the subject will undergo the following assessments:

- Adverse events, medications, laboratory tests and 12-lead ECGs (if performed)

A subject will be considered ‘Lost to Follow-up’ after 2 consecutive missed visits and a minimum of two unsuccessful phone calls from investigational site personnel to the subject or contact to schedule the next follow-up visit. These two phone calls must be documented in the subject records. If the subject is deemed lost to follow-up a letter must be sent to the subject’s last known address or to the subject’s general

practitioner (GP) or family physician and a copy of the letter must be maintained in the subject's hospital records.

## **6.13 Study Committees**

### **6.13.1 Steering Committee (SC)**

A Steering Committee will advise the Sponsor on key aspects related to the development, execution, analysis and reporting, and overall conduct of the clinical investigation. A Steering Committee charter will define membership of the committee and outline the purpose, roles, responsibilities, and general rules of operation for the Steering Committee. This charter is maintained by the Sponsor and sets forth the procedures for the implementation of the Steering Committee.

### **6.13.2 Publication Committee (PC)**

A Publication Committee shall be established to oversee study publications. Publication Committee membership may include members of the Steering Committee, investigators, representative(s) of Abbott and statisticians. The Publication Committee will be responsible for identifying, selecting and approving publication proposals and determining authorship according to a Publication Plan. A Publication Committee charter will define membership of the committee and outline the roles and responsibilities of the committee, as well as rules to define authorship.

### **6.13.3 Data Safety Monitoring Board (DSMB)**

An independent DSMB will review on a regular basis accumulating data from the clinical investigation and will advise the Sponsor regarding the continuing safety of subjects and those yet to be recruited, as well as the continuing validity and scientific merit of the clinical investigation. DSMB members will not be investigators in the clinical investigation. At any time during the investigation, the DSMB may offer opinions or provide formal recommendations concerning aspects of the study that impact subject safety (e.g. safety-related protocol changes or input regarding study-related adverse event rates).

All events associated with the baseline imaging and or stenting procedure will be reported to the Data and Safety Monitoring Board (DSMB) and reviewed on a regular basis. The DSMB may request additional information as needed. Based on safety data, the DSMB may recommend to the Sponsor and Steering Committee to stop or otherwise modify the study. The Sponsor will make the final decision after weighing the recommendation of the DSMB whether the study should then be stopped, modified or continued without change. The DSMB procedures will be described in the DSMB Charter.

The primary function, responsibilities and membership of the DSMB will be described in detail in a DSMB charter.

### **6.13.4 Clinical Events Committee (CEC)**

An Independent Clinical Events Committee (CEC) will be established and will be comprised of interventional and/or non-interventional cardiologists who are not participants in the study and are independent from the study. The CEC will review death, MI, stent thrombosis, repeat revascularizations, and intra-procedural complications (to determine their relationship to the imaging catheter). The CEC will also adjudicate the coronavirus disease 2019 (COVID-19) relatedness of a clinical endpoint event. The Committee procedures will be specified in the CEC charter.

## 7 Statistical Considerations

The following section describes the statistical methods for the clinical investigation and justification of the design. Additional details on statistical analyses, including sensitivity analyses, poolability analyses, subgroup analyses and analysis of descriptive endpoints are maintained in a separate Statistical Analysis Plan (SAP).

### 7.1 Endpoints

#### 7.1.1 Primary Endpoint of MSA and Hypothesis

The primary endpoint of MSA is Post-PCI MSA measured by OCT in each randomized arm, as measured at the Cardiovascular Research Foundation OCT Core laboratory, which is blinded to imaging modality assignment.

Let  $M(\text{OCT})$  be the mean MSA in OCT-guided arm, while  $M(\text{Angio})$  is mean MSA in angiography-guided arm. The following hypothesis will be tested:

$$H_0: M(\text{Angio}) - M(\text{OCT}) \geq 0$$

$$H_1: M(\text{Angio}) - M(\text{OCT}) < 0$$

The null hypothesis will be tested at the one-sided 2.5% significance level [REDACTED]

##### 7.1.1.1 Analysis Methodology

##### 7.1.1.2 Sample Size Determination

[REDACTED] a sample size of 1600 randomized subjects will provide at least 95% power to demonstrate superiority of treatment.

##### 7.1.1.3 Analysis Population

The primary endpoint of MSA will be tested in all randomized subjects in whom one or more stents were implanted at a target lesion. Subjects who were randomized but in whom a stent was not implanted at a target lesion will be excluded.

#### 7.1.2 Primary Endpoint of TVF and Hypothesis

The co-primary effectiveness endpoint is the rate of target vessel failure (the composite of cardiac death, target vessel MI (per primary protocol definition [see Appendix B]) and ischemia-driven target vessel

revascularization) at 2 years. For patients with multiple target vessels, TVF in either or both target vessels constitutes an endpoint event.

The following hypothesis will be tested for the analysis on TVF.

$$H_0: H(\text{OCT}) / H(\text{Angio}) \geq 1$$

$$H_1: H(\text{OCT}) / H(\text{Angio}) < 1$$

where H(OCT) and H(Angio) are hazard function for the OCT-guided arm and angiography-guided arm. The null hypothesis will be tested at the one-sided 2.5% significance level.

[REDACTED]

#### 7.1.2.1 Analysis Methodology

[REDACTED]

[REDACTED]

#### 7.1.2.2 Sample Size Determination

[REDACTED] will provide 90% power at a one-sided significance level of 0.025, which is associated with approximately 2490 subjects. If an interim analysis indicates a sample size increase, the enrollment can be adjusted up to a total of 3656 subjects.

#### 7.1.2.3 Analysis Population

The primary endpoint of TVF will be tested in all randomized subjects by intention-to-treat; subjects will be analyzed according to their randomized group regardless of the device attempted or implanted.

#### 7.1.3 Major Secondary Endpoint of TVF Excluding Periprocedural MI and Hypothesis

The major powered secondary endpoint is the rate of target vessel failure excluding periprocedural MI (the composite of cardiac death, target vessel-related spontaneous MI or ischemia-driven target vessel revascularization). For patients with multiple target vessels, TVF excluding periprocedural MI in either or both target vessels constitutes an endpoint event.

The following hypothesis will be tested for the analysis on TVF excluding periprocedural MI.

$$H_0: H(\text{OCT}) / H(\text{Angio}) \geq 1$$

$$H_1: H(\text{OCT}) / H(\text{Angio}) < 1$$

where H(OCT) and H(Angio) are hazard function for the OCT-guided arm and angiography-guided arm. The null hypothesis will be tested at the one-sided 2.5% significance level.

[REDACTED]

[REDACTED]

- [REDACTED]
- [REDACTED]
- [REDACTED]
- [REDACTED]

[REDACTED] a total sample size of 2490 subjects with 2-year follow-up will provide [REDACTED] approximately 85% power to reject the null hypothesis at a one-sided alpha of 2.5%.

### 7.1.3.1 Analysis Methodology

[REDACTED]

[REDACTED]

[REDACTED]

[REDACTED]

[REDACTED]

[REDACTED]

[REDACTED]

[REDACTED]

### 7.1.3.2 Analysis Population

The powered secondary endpoint of TVF excluding periprocedural MI will be tested in all randomized subjects by intention-to-treat; subjects will be analyzed according to their randomized group regardless of the device attempted or implanted.

## 7.2 Justification of Clinical Investigation Design

This is a prospective single-blind clinical investigation randomizing subjects between OCT-guided coronary stent implantation and angiography-guided coronary stent implantation. Subjects will be randomized in a 1:1 ratio. There are two primary endpoints of the study. The primary imaging endpoint is the acute post-procedural MSA (per target lesion basis) by OCT-guided-PCI compared to angiography-guided PCI. The MSA is a rationale primary endpoint as the most consistent and strongest parameter to predict clinical outcomes is the post-PCI MSA. In the present study, after 1600 randomized subjects are enrolled with procedure completed, the primary endpoint of MSA will be tested to compare OCT-guided and angiography-guided arms and reviewed by the DSMB . If significantly larger MSA in OCT-guided arm is demonstrated, the DSMB will recommend that the trial will continue enrolling subjects (and the data will be kept blinded). Otherwise the acute OCT data will be unblinded to the Steering Committee and a decision will be made whether to stop the trial for futility, considering all imaging data available. No imaging data will be made public unless the trial is terminated prematurely for futility. Similarly, the Steering Committee will not be unblinded to any clinical data unless the decision is made to stop the trial prematurely.

The primary clinical endpoint is target vessel failure (cardiac death, TV-MI, or ischemia-driven TV-revascularization). TVF is a rationale co-primary endpoint as it is a clinical outcome which directly links the treatment effect to long-term clinical outcomes.

### 7.3 Overall Sample Size

The sample size required for evaluation of the first primary endpoint of MSA is 1600 randomized subjects, while the sample size for the primary endpoint [REDACTED] (approximately 2490 subjects). If an interim analysis suggests a sample size increase, up to a maximum of 3656 subjects will be randomized.

### 7.4 Timing of Primary Endpoint Analysis

There will be two analyses planned in the trial. The interim analysis of MSA will be conducted when 1600 randomized subjects are enrolled with procedures completed. If the superiority in the OCT-guided arm is demonstrated, the second analysis of TVF will be implemented when the pre-specified number of adjudicated TVF events are reached.

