The Clinical Events Committee (CEC) may not be blinded to the randomization assignment in all patients. The angiographic core laboratories may not be blinded to treatment strategy in all patients. The Data Safety Monitoring Board (DSMB) will be blinded to the subject's randomization. Independent statisticians will generate blinded tables for review by the DSMB. The DSMB may request unblinded data if a safety signal is observed.

Sponsor personnel that will be unblinded will be the independent biostatisticians involved in generating and verifying the randomization code, key Clinical Science and Operations, Clinical Safety Monitors, Site Monitors, Clinical Data Management, Electronic Database Programmer, Inventory Management staff, and Clinical Information System (IS) personnel working on the trial. Restricted access of blinded personnel to the clinical database will be maintained until unblinding of the study for analysis of the primary clinical outcome at 2 years, described below in **Section 5.3.1**.

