### 5.3.1 Primary Endpoints

1. Imaging Outcome (powered): Minimal stent area (MSA), continuous measure

Final Post-PCI MSA (per target lesion basis) assessed by OCT in each randomized arm, measured at an independent OCT core laboratory blinded to imaging modality assignment.

2. Clinical outcome (powered): Target vessel failure (TVF)

Time-to-first event rate of the composite outcome of cardiac death, target vessel myocardial infarction (TV-MI) (per primary protocol definition [see Appendix B]), or ischemia-driven target vessel revascularization (ID-TVR), assessed at 2 years.

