#### 6.5.5 Scheduled Follow-ups

All patients enrolled in the study will be followed with clinic visit or phone calls at 30 ( $\pm$ 7) days, 1 year ( $\pm$ 30 days) and 2 years ( $\pm$ 30 days) by the authorized study personnel at the study site.

- 30-day Follow-Up

Telephone or clinic visit follow-up at 30 days ( $\pm$  7 days) including:

- Adverse events, medications, laboratory tests and 12-lead ECGs (if performed)
- 12 Month Follow-Up  
Telephone or clinic visit follow-up at 12 months ( $\pm$  30 days) including:
  - Adverse events, medications, laboratory tests and 12-lead ECGs (if performed)
- 24 Month Follow-Up  
Telephone or clinic visit follow-up at 24 months ( $\pm$  30 days) including:
  - Adverse events, medications, laboratory tests and 12-lead ECGs (if performed)

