- If the first creatinine draw indicates contrast induced nephropathy (absolute increase  $>0.5$ mg/dl (44.2 $\mu$ mol/L) or  $>25\%$  or the pre-procedure value) it is recommended that creatinine be drawn daily until the peak is reached and the creatinine is decreasing. If the subject develops overt bleeding, or the hemoglobin level has fallen more than 3 g/dL (30 g/L) in the absence of overt bleeding, serial hemoglobin levels must be drawn at least daily until a nadir is reached or the hemoglobin level has stabilized.

 Office visit or Telephone when last subject enrolled reached 12-month follow-up, excluding subjects with follow-up completed within 30 days

 Blinded

 Required at baseline in subject in whom randomization is likely or definite, optional at post-procedure

 Roll-In subjects are followed through post-procedure visit

 For unscheduled visits, procedure details, tests and medications will not be recorded in the database

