3.0 TRIAL DESIGN

This is a prospective, single-blind clinical investigation randomizing subjects to OCT-guided coronary stent implantation vs. angiography-guided coronary stent implantation in a 1:1 ratio. The clinical investigation will be conducted at approximately 125 centers in North America (US and Canada), Western Europe, and Asia-Pacific. Up to 3656 randomized subjects and approximately 375 roll-in subjects will be enrolled in the clinical investigation. No site may enroll more than 15% of the total subjects. Subjects participating in this clinical investigation will be followed for 2 years. The expected duration of enrollment is approximately 2 years. The total duration of the clinical investigation is expected to be approximately 5 years.

The sample size is driven by the primary endpoint of target vessel failure (TVF). Because of the event driven nature of this primary endpoint, the statistical power of the trial is a function of the number of endpoint events, and not a direct function of the number of patients enrolled. As a result, the number of patients is not an endorsement of the statistical power of the trial. If event rates are lower than anticipated, more patients will be required to obtain a sufficient number of endpoint events.

Subjects will be randomized in a 1:1 ratio according to an electronic randomization system. Randomization will be stratified by medically treated diabetes, presentation with a biomarker positive ACS (NSTEMI or recent STEMI), and site.

Each operator will complete OCT-guided stenting roll-in cases (up to 3, if needed) according to a pre-specified stent optimization protocol on patients meeting study inclusion/exclusion criteria. Within 72 hours of receipt, the core lab will determine accurate OCT measurements and stent optimization protocol compliance. OCT Core laboratory approval of each operator is required to proceed to the randomization phase.

Subjects will be considered enrolled in the trial once informed consent has been obtained and the subject is randomized. The trial will utilize a Clinical Events Committee (CEC) to review adverse events for adjudication of trial endpoints.

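### Does Protocol 7.4 leave it open whether the TVF data are cut at an event count or after two years of follow-up?

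*Protocol*

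**What the plan says.** - Protocol 7.4 plans two analyses: MSA after 1600 randomized subjects, and then TVF. On the timing of the latter it says only that "the second analysis of TVF will be implemented when the pre-specified number of adjudicated TVF events are reached".
- Protocol 5.3.1 defines TVF as a time-to-first-event composite ending with "ischemia-driven target vessel revascularization (ID-TVR), assessed at 2 years". Section 6.11 states: "Subject participation in the clinical investigation will conclude upon completion of the 24-month visit". Section 5.1.1 says that restricted database access "will be maintained until unblinding of the study for analysis of the primary clinical outcome at 2 years".
- For the major secondary endpoint, Protocol 7.1.3 states that "a total sample size of 2490 subjects with 2-year follow-up will provide" about 85% power.
- SAP 3.0 calls the TVF endpoint event driven and adds: "If event rates are lower than anticipated, more patients will be required to obtain a sufficient number of endpoint events". Protocol 7.1.2.2 and 7.3 allow an increase from about 2490 to at most 3656 subjects.
- Footnote 7 in Protocol 6.8 reads: "Office visit or Telephone when last subject enrolled reached 12-month follow-up, excluding subjects with follow-up completed within 30 days". In the table as extracted, it is attached to the 30-day and 12-month columns. Section 6.5.5 lists contacts at 30 days, 1 year and 2 years only.
- Protocol 7.1.2.1, 7.6 and 7.9, SAP 5.3.2 and part of SAP 5.3.3 are redacted. SAP 5.6 (Interim Analysis) shows no readable text.

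**The concern.** Someone looking for the TVF data cut finds an event count in one place, two years in several others, and a date tied to the last subject's 12 months in a footnote. Section 7.4 does not relate them. If events ran ahead of plan, the count could be reached while many subjects were still in their second year and between scheduled contacts. If events ran behind, the readable text does not say what happens once the last subject has finished 24 months. The footnote makes this look worse, because it cannot describe a 30-day visit and could be taken as a close-out contact for an earlier cut. At stake would be how complete the second-year data are, the power of the major secondary endpoint if it is read at the same cut, and clear instructions to sites.

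**Working it through.** **1. What each statement governs.**

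| Statement | Governs |
|---|---|
| Event count (Protocol 7.4) | When the TVF analysis is run |
| 2 years (5.3.1), 24-month visit (6.11) | How long one subject can contribute |
| Contact at last subject's 12 months (6.8, footnote 7) | A contact; no analysis or cut is named, and subjects with follow-up completed within 30 days are exempt |

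The first two operate together by censoring each subject at the earlier of 24 months and the cut. The third is not a rule about the TVF data.

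**2. The plan's own figure.** About 2490 subjects for 90% power at one-sided 0.025 cannot be reproduced, because the hazard ratio, event rates and event count are redacted. Over an assumed range, with 1:1 allocation, the required events are D = 4(1.960 + 1.2816)² / (ln HR)²:

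| Assumed HR | Events D | D/2490 |
|---|---|---|
| 0.60 | 162 | 6.5% |
| 0.65 | 227 | 9.1% |
| 0.70 | 331 | 13.3% |
| 0.75 | 508 | 20.4% |
| 0.80 | 845 | 33.9% |

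The formula contains no follow-up term. At the planned count, power is Φ(3.2416 − 1.960) = Φ(1.2816) = 90%, however many subjects have reached 24 months.

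**3. Calendar.** SAP 3.0 expects about 2 years of enrollment and about 5 years in total. Full follow-up ends at 24 + 24 = 48 months, about 12 months inside 60. SAP 5.3.1 tests TVF only in the final analysis. Both are compatible with full two-year follow-up.

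**4. Count reached early (illustration).** Assume that 2490 subjects followed for 2 years yield exactly the target, that accrual is uniform over 24 months, that a share s of 10–30% of events falls at the procedure, and that the rest are spread evenly. If the rate is 20% above plan, the cut comes when the average subject has accrued 1/1.2 = 83.3% of their 2-year events. That is month 31–33, with 31–39% of subjects at 24 months (0.31 × 2490 = 772 to 0.39 × 2490 = 971, ignoring dropout). The TVF test still has its full count.

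If the major secondary were read at that cut, its events relative to plan would be (1 − 1.2s)/(1 − s), which is 0.978 at s = 0.1 and 0.914 at s = 0.3. Power is Φ(√ratio × (1.960 + 1.036) − 1.960), or 84% to 82%, against the stated 85%.

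**5. Count reached late or not at all.** On the same assumption about the target, 3656 subjects are expected to supply it as long as the event rate is at least 2490/3656 = 68% of plan. At an unchanged accrual rate, enrolling 3656 takes 24 × 3656/2490 = 35.2 months. With a rate 20% below plan, the count then arrives at month 40–43, with 46–53% of subjects at 24 months. If the count still falls short, power at a fraction f of the planned events is Φ(3.2416√f − 1.960):

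- f = 0.9: Φ(1.115) = 86.8%
- f = 0.8: Φ(0.939) = 82.6%

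**6. A cut at the footnote's date.** Month 24 + 12 = 36 would have (36 − 24)/24 = 50% of subjects at 24 months. Under a constant hazard with a 6–14% two-year rate, about 88% of the target events would have occurred, and power would be Φ(3.2416√0.88 − 1.960) = 86%. No section proposes a TVF cut at that date, so this is not a property of the plan.

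**The case for a change.** The strongest argument for a change is that the cut for a confirmatory endpoint should be readable in the section that gives its timing. The sponsor states one elsewhere: SAP Appendix C ties the ISR analysis to the last subject's two years. The major secondary is powered on two-year follow-up, so an early cut would cost it a little. If the treatment effect changes over time, an early cut also gives more weight to procedural and first-year events, and the 90% figure in step 2 assumes that it does not. The remedy in SAP 3.0, more patients, does not help once enrollment has closed. Footnote 7 is unredacted and matches no contact in 6.5.5.

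Part of this stands. The public 7.4 does not say whether the cut also waits for full follow-up, and it gives no fallback. The purpose of footnote 7 is unclear, even if its column markers are an extraction artefact.

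The rest does not amount to a defect. A trigger and a horizon are not in conflict. Cutoff, censoring and fallback rules would normally sit in the sections that are redacted here. Prescribing a rule is not free either: requiring completed 24-month follow-up would move the cut in step 4 from month 31–33 to month 48. That is a choice for the sponsor, not a correction.

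**Conclusion.** No change follows. Followed as written, 7.4 gives a valid test at the planned number of events, with each subject counted for up to two years. The readable text leans towards full follow-up: 5.1.1 speaks of the outcome at 2 years, TVF is tested only in the final analysis, and the total duration leaves room for it. What remains is a detail that the redacted sections may already settle and that analysts would otherwise handle by censoring at the earlier of 24 months and the cut. Footnote 7 is an unexplained contact, plausibly a clerical leftover, with no stated bearing on the TVF analysis.

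The size is small. There is no loss for TVF at the planned count, about 1 to 3 percentage points for the major secondary in the 20%-higher illustration, and TVF power of about 87% or 83% if 10% or 20% of the planned events never occur. These figures rest on proportional hazards, an event target equal to the yield of 2490 subjects and, for the major secondary, uniform accrual and an assumed 10–30% procedural share. None of them can be checked against the redacted event target or the redacted sample-size rule.
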